4.4. Study Duration

Subjects will be deemed enrolled once they sign informed consent and meet all inclusion and no exclusion criteria and complete all screening assessments. The study duration of subject participation from Screening through ¹⁸F-DCFPyL PET/CT imaging and Efficacy visit(s), if applicable, will be a maximum duration of approximately 12 months. At a minimum, all subjects who receive a dose of ¹⁸F-DCFPyL will be followed from time of informed consent until the safety phone call on Day 8 (± 3).

Only subjects with positive PyL PET/CT scans (detection of disease at any site) will be followed at the Efficacy visit(s). Subjects will undergo Efficacy assessments based on the site's local PyL PET/CT interpretation and clinical presentation.

- Subjects with any positive PyL PET/CT finding(s) per local interpretation will be evaluated as described in [Section 4.3.5](#).
- Subjects without any positive PyL PET/CT finding per local interpretation will complete the study through the safety phone call; no further visits will be required.

The Sponsor may conclude the study before subjects complete their efficacy follow-up assessments (see [Section 10.4.2](#))

4.5. Safety Monitoring

An independent Data Monitoring Committee (DMC) will not be used for this open-label study. However, safety monitoring will consist of continuously monitoring adverse events on an ongoing basis in accordance with [Section 9](#). A safety review committee, consisting of Sponsor representatives (e.g., Medical Monitor, Clinical, Drug Safety) will also review data on an ongoing basis to assess subject safety and eligibility through listings, tables and subject profiles.

4.6. Criteria for Study Termination

The Sponsor reserves the right to terminate the study at any time. In the event of serious, unexpected and related adverse events, the program may be stopped prematurely upon advice from the Safety Review Committee, the Sponsor or upon request from the FDA. In addition, the Sponsor or the Institutional Review Board (IRB) or Independent Ethics Committee (IEC) may terminate an investigational site for the following (but not limited to) reasons:

- If any significant safety issues occur;
- Failure of the Investigator to comply with pertinent International Conference on Harmonisation (ICH) E6 guidelines on Good Clinical Practice (GCP) guidelines and regulations;
- If significant protocol violations occur;
- Submission of knowingly false information from the research facility to the Sponsor, Clinical Monitor, or other party involved in the study;
- Failure of the Investigator to enroll subjects into the study at an acceptable rate as agreed-upon with the Sponsor

Table 3: Schedule of Assessments

Day	Screening	¹⁸ F-DCFPyL Dosing & Imaging		Safety Phone call ³	Efficacy follow-up ⁴	
	-30 to 1	1	1 (60-120 min post-dosing)	8 (±3)	2 to 60	Every 3 months following initiation of locoregional RT, up to 9 months ⁷
Informed Consent & Eligibility	X					
Demographics	X					
Medical History	X					
Prior Medications and Prior Cancer Treatments	X					
Vital Signs (blood pressure, heart rate)		X (pre-dosing)	X			
PSA (Total)	X ¹					X ^{1,7}
Conventional imaging	X ²				X ⁶	
¹⁸ F-DCFPyL Administration		X				
Whole body PyL PET/CT			X			
Surgery or image-guided biopsy & histopathology					X ⁵	
Locoregional radiation therapy per investigator discretion					X ⁷	
Treatment-emergent Adverse Events			X	X		
Concomitant Medications and Procedures			X	X	X	X
Medical Management Questionnaire	X ⁸				X ⁹	

- Total PSA will be collected and sent to central lab for analysis. If done on Day 1 of Screening, the blood draw should be collected prior to ¹⁸F-DCFPyL dosing.
- Applicable conventional imaging performed as part of standard of care workup within 60 days prior to Day 1.
- A safety phone call will occur 7 (±3) days post-¹⁸F-DCFPyL dosing if Efficacy follow-up has not yet occurred.
- Efficacy follow-up visit(s) are only applicable for subjects with positive ¹⁸F-DCFPyL PET/CT finding(s) per local interpretation
- Surgery or biopsy to occur at least 12 hours from time of ¹⁸F-DCFPyL dosing but not more than 60 days following ¹⁸F-DCFPyL PET/CT imaging. Imaging used to guide biopsy (e.g., CT, MRI-TRUS, US) will be submitted to the central core imaging lab.
- Follow-up conventional imaging (e.g., targeted MRI/CT, fluciclovine or choline PET) per Investigator's discretion of the anatomical correlate to the lesion(s) identified on ¹⁸F-DCFPyL PET/CT is required in subjects whom evaluable histopathology for prostate cancer is not available. The image(s) will be submitted to the central core imaging lab for review and determination of evaluability.
- If evaluable histopathology result for prostate cancer is not available and follow-up conventional imaging of the PyL-suspected lesion is not informative, subjects initiated on locoregional radiation therapy (RT) alone within 60 days following PyL PET/CT (with no concomitant ADT administered during this time) will be followed every 3 months (± 7 days), up to 9 months post-initiation of RT. PSA response (decline of ≥50% from baseline PSA) must be confirmed (two consecutive levels within 4 weeks) per central lab evaluation.
- Pre-PyL Medical Management Questionnaire (MMQ) will be completed by the treating investigator for all subjects enrolled (who signed informed consent and met all eligibility criteria) in the study prior to Day 1.
- Post-PyL MMQ will be completed by the treating investigator for all subjects who completed ¹⁸F-DCFPyL PET/CT imaging.

5. SUBJECT SELECTION AND WITHDRAWAL CRITERIA

5.1. Subject Inclusion Criteria

Subjects must meet all of the following inclusion criteria:

1. Male \geq 18 years of age
2. Histopathologically confirmed prostate adenocarcinoma per original diagnosis, with subsequent definitive therapy
3. Suspected recurrence of prostate cancer based on rising PSA after definitive therapy on the basis of:
 - a. Post-radical prostatectomy (RP): Detectable or rising PSA that is \geq 0.2 ng/mL with a confirmatory PSA \geq 0.2 ng/mL (American Urological Association [AUA] recommendation)³⁹; or
 - b. Post-radiation therapy (RT), cryotherapy, or brachytherapy: Increase in PSA level that is elevated by \geq 2 ng/mL above the nadir (American Society for Therapeutic Radiology and Oncology [ASTRO]-Phoenix consensus definition)⁴⁰
4. Negative or equivocal findings for prostate cancer on conventional imaging performed as part of standard of care workup within 60 days prior to Day 1
5. Life expectancy \geq 6 months as determined by the investigator
6. Able and willing to provide informed consent and comply with protocol requirements

5.2. Subject Exclusion Criteria

Subjects meeting any of the following exclusion criteria are not eligible for this study:

1. Subjects administered any high energy (>300 KeV) gamma-emitting radioisotope within five (5) physical half-lives prior to Day 1
2. Ongoing treatment with any systemic therapy (e.g., androgen deprivation therapy [ADT], antiandrogen, GnRH, LHRH agonist or antagonist) for prostate cancer
3. Treatment with ADT in the past 3 months of Day 1
4. Receipt of investigational therapy for prostate cancer within 60 days of Day 1
5. Subjects with any medical condition or other circumstances that, in the opinion of the investigator, compromise the safety or compliance of the subject to produce reliable data or completing the study

5.3. Subject Withdrawal Criteria

A subject may withdraw from the study at any time for any reason without prejudice to his future medical care by the physician or at the study site. Likewise, the Investigator and/or Sponsor

have the right to withdraw patients from the study. Subjects may be discontinued for any of the following reasons:

- Significant protocol violation or noncompliance
- Adverse event that precludes further study participation
- Best medical interest of the patient (Investigator decision)
- Sponsor terminates the study
- Subject requests to be withdrawn from the study
- Subject is lost to follow-up
- Death

Should a subject withdraw from the study, all efforts will be made to complete the required study procedures as thoroughly as possible prior to withdrawal.

Data will be collected for all withdrawn subjects up until the time of discontinuation. The reason for discontinuation from the study will be recorded in the subject's eCRF.

6. TREATMENT OF SUBJECTS

6.1. Description of Study Drug

A single administration of ¹⁸F-DCFPyL Injection will be administered prior to PET/CT imaging on Day 1.

Table 4: Investigational Product

Product Name	¹⁸ F-DCFPyL INJECTION
Dosage Form	Sterile solution for intravenous injection
Unit Dose	9 mCi (333 MBq) at the Time of Administration
Route of Administration	Intravenous catheter placed in an antecubital vein or an equivalent venous access
Physical Description	Colorless, particle-free solution

6.2. Concomitant Medications and Procedures

All concomitant medications and medical procedures will be recorded in the eCRF from post-¹⁸F-DCFPyL dosing (Day 1) and at all subsequent study visits as shown in [Table 3](#) Schedule of Assessments.

Any new or changed medications, including prostate cancer therapy, from time of ¹⁸F-DCFPyL injection to each study visit must be recorded in the eCRF. Subjects who receive concomitant systemic or investigational therapy for prostate cancer anytime during participation in the study will be discontinued from the study.

6.3. Treatment Compliance

All ¹⁸F-DCFPyL injections will be administered under the supervision of the investigator or qualified designee. Details of the study drug injection will be captured in each subject's source documents.

6.4. Randomization and Blinding

This is an open-label, non-randomized study.

Independent readers from a central imaging core lab will be given access to ¹⁸F-DCFPyL PET/CT, biopsy-guided imaging (if performed), and follow-up conventional imaging (if performed). The central readers will be blinded to all other clinical information and histopathology results (if available).

Institutional staff may review all local images in conjunction with available clinical information to permit clinical management planning for the subject. The informed consent form (ICF) must include language of potential changes to the medical management plan for the subject.

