8.2. Image Acquisition

Central imaging core lab readers will independently assess all PyL PET/CT images as well as any subsequent conventional images performed following PyL PET/CT.

8.2.1. Follow-up conventional imaging to verify PyL-suspected lesion(s) within 60 days following ¹⁸F-DCFPyL PET/CT

Within 60 days following ¹⁸F-DCFPyL PET/CT imaging, if a positive lesion(s) is identified on ¹⁸F-DCFPyL PET/CT and tissue acquisition of the PyL-suspected lesion is not feasible, then conventional imaging (e.g., targeted MRI or CT, fluciclovine or choline PET) will be performed in an attempt to anatomically correlate the PyL-suspected lesion(s). All follow-up imaging will be sent to the central imaging core lab. The choice of the most appropriate conventional imaging modality will be at the discretion of the investigator; use of the most sensitive imaging method is encouraged, such as targeted MRI for verification of the PyL-suspected bone lesion(s).

If tissue acquisition (by surgery or biopsy) of the PyL-suspected lesion is feasible, then see [Section 8.4 Histopathology](#).

8.2.2. ¹⁸F-DCFPyL PET/CT Imaging

Prior to enrollment, all PET/CT scanners to be used in this study must be qualified in accordance with the procedures outlined in the [Imaging Manual](#).

¹⁸F-DCFPyL PET/CT imaging will be performed using local PET/CT scanners with low dose CT for attenuation correction and anatomic localization as described in the [Imaging Manual](#). Subjects will be asked to void prior to imaging. After voiding, a whole-body CT and PET scan will be acquired starting from the mid-thigh through the skull. Whole body PET/CT scans must be obtained within 60-120 minutes following the ¹⁸F-DCFPyL dosing.

All ¹⁸F-DCFPyL PET emission data should be acquired and reconstructed in accordance with the [Imaging Manual](#).

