8.3. Image Interpretation by Central Imaging Core Lab

The central imaging core lab will receive and evaluate all conventional images and PyL PET/CT scans, as applicable. Imaging data will be anonymized at the site upon image submission to the central lab and prepared for reading. PET data will be interpreted by three different independent readers in a random order at separate reading sessions. Cross sectional CT imaging from the PET/CT scans will be available for anatomic correlation. Central imaging core lab readers will be blinded to all clinical data, including PSA and histopathology (if available).

The processes for image acquisition, transmittal and interpretation are detailed in the [Imaging Manual](#) and [Imaging Review Charter](#) documents.

8.4. Histopathology from Biopsy or Surgery (if performed) of PyL-positive lesion(s) within 60 days following ¹⁸F-DCFPyL PET/CT

Within 60 days following PyL PET/CT imaging and prior to initiation of any new systemic or radiation PC therapy, if a PyL-positive lesion is identified per the site's image interpretation, tissue acquisition via surgery or image-guided biopsy should be performed if clinically feasible.

Immediately following biopsy or surgery, the specimens will be sent for local histopathological processing and analysis at the site in accordance with the study [Pathology Manual](#). Procedures and results will be recorded in the eCRF. See [Section 8.4](#) for histopathology processing and analysis at the site. If the subject's histopathology result is evaluable for prostate cancer, then no further visits are required for the subject. If histopathology is not evaluable, then see [Section 8.2.1](#) for required conventional imaging follow-up.

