4. STUDY DESIGN

This is a phase 3, multi-center, open-label, single-arm, non-randomized study to evaluate the diagnostic performance and safety of ¹⁸F-DCFPyL (PyL) PET/CT in subjects with suspected recurrence of prostate cancer and negative or equivocal findings per institutional standard of care conventional imaging. This study is planned to be conducted in approximately 15 sites in the United States and Canada, and to be conducted in conformance with Good Clinical Practices (GCP).

Eligible subjects will be enrolled in a non-randomized, sequential manner, with competitive enrollment between study sites. Enrolled subjects will receive a single dose of 9 mCi (333 MBq) ¹⁸F-DCFPyL Injection followed by a single PET/CT scan acquired at 1-2 hours post-dosing.

Only subjects with positive ¹⁸F-DCFPyL PET/CT scans per local interpretation (detection of disease at any location) will be followed for Efficacy follow-up visit(s) (See Table 1 Schedule of Assessments). ¹⁸F-DCFPyL PET/CT scans will be evaluated by three independent central readers blinded to all clinical and other imaging information. ¹⁸F-DCFPyL PET/CT imaging results reported by the central readers will be compared to the composite truth standard of histopathology where available, imaging follow-up, or treatment response as defined in Section 5.1.1.

Once the study reaches the required number of subjects evaluable for calculation of the primary endpoint as described in Section 7.1, subject enrollment and follow-up assessments will conclude, and the study database will be locked for analysis. Adverse events (AEs) will be assessed following ¹⁸F-DCFPyL dosing (Day 1), and again via a safety phone call 7 (±3) days post-¹⁸F-DCFPyL dosing to capture any late-occurring AEs.

Medical Management Questionnaires (MMQs) will be completed by the treating investigator at two time-points during the study to capture planned changes in the clinical management for all subjects who underwent ¹⁸F-DCFPyL PET/CT imaging:

- **Prior to** ¹⁸**F-DCFPyL dosing,** the treating investigator will complete the Pre-PyL MMQ based on baseline clinical information and results from conventional imaging.
- **Post-**¹⁸**F-DCFPyL imaging**, the treating investigator will complete the Post-PyL MMQ based on the additional result from local interpretation of the ¹⁸F-DCFPyL PET/CT scan, to assess whether a planned change to the initial medical management plan is warranted due to the PyL finding.

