5. STUDY ENDPOINTS

5.1. Efficacy Endpoints

Efficacy endpoints that reference ¹⁸F-DCFPyL PET/CT imaging findings are based on imaging results as reported by central imaging review by three independent, blinded central readers. The primary endpoint of CLR and the exploratory PPV endpoints are also based on the assessments made by the Imaging Truth Panel (a consensus of two readers distinct from the independent central PyL readers). See the study Imaging Review Charter for read paradigm and details. The change in clinical management endpoint is based on investigator assessment of local ¹⁸F-DCFPyL PET/CT imaging findings.

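### The protocol lets the central readers see the biopsy-guidance and follow-up images, while the SAP blinds the PyL readers to them; if the protocol wording were followed, the CLR would be open to review bias.

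*Protocol*

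**What the plan says.** Protocol 6.4 describes one group, independent readers from the central imaging core lab. It gives them the PyL PET/CT together with "biopsy-guided imaging (if performed), and follow-up conventional imaging (if performed" and then limits the masking: "The central readers will be blinded to all other clinical information and histopathology results (if available". Other imaging is not on the masked list.

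Protocol 8.2 points the same way: "Central imaging core lab readers will independently assess all PyL PET/CT images as well as any subsequent conventional images performed following PyL PET/CT". Protocol 8.3 describes the PET read ("PET data will be interpreted by three different independent readers in a random order at separate reading sessions") and restates the masking ("Central imaging core lab readers will be blinded to all clinical data, including PSA and histopathology (if available"), again without mentioning other imaging. It also says that the PET/CT's own CT is available for anatomic correlation.

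The SAP describes a different arrangement. Under SAP 4, the PyL scans "will be evaluated by three independent central readers blinded to all clinical and other imaging information". Under SAP 5.1, the CLR also rests on an Imaging Truth Panel, defined as "a consensus of two readers distinct from the independent central PyL readers", with the Imaging Review Charter cited for details. The protocol does not name this panel.

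**The concern.** The CLR compares a test location with a truth location. Follow-up conventional imaging is the second tier of the composite truth standard (protocol 8.1). Biopsy-guidance images are used to confirm that the sampled site is the PyL lesion (protocol 8.2.3). SAP 8.5.2.1 and Table 4 make the subject a true or false positive according to whether the central reader's location matches the truth location. A reader who has already seen the CT or MRI correlate, or the needle position, can be steered towards it, and test and truth are then no longer independent.

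Timing adds to this. Protocol 4.1 and 4.3.5.1 have the core lab judge follow-up scans while the trial is running, because that judgement decides whether a subject completes the study or may go on to PSA follow-up. The protocol has no rule that PyL reads come first or are closed before those images are opened.

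**Working it through.** **Who may see what**

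| Item | Protocol 6.4, 8.2, 8.3 | SAP 4, 5.1 |
|---|---|---|
| Images available | PyL PET/CT, biopsy guidance, follow-up conventional | PyL readers: no other imaging |
| Masked to | Clinical data, PSA, histopathology | All clinical and other imaging information |
| Who reads the follow-up images | Core lab readers, not separated by role | Two-reader Truth Panel, distinct from the PyL readers |
| Order of reads | Separate PET sessions, random order; nothing on truth images | Referred to the Charter |

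Taken literally, the protocol permits what the SAP forbids.

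**Where exposure could change the outcome (SAP Table 4 and 5.1.3)**

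- Correlative imaging: a positive result with a location match is a true positive; without a match it is a false positive. A reader prompted by the image can turn a mismatch into a match. A reader who has seen a negative result could also call the scan negative, which moves a false positive out of the CLR denominator. This is the clearest upward path.
- Image-guided biopsy: pathology stays masked. A lesion placed at the needle site becomes a true positive if pathology is positive and a false positive if it is negative. If the needle is not in a PyL-positive lesion, the subject goes to another truth standard. The direction is not uniform.
- Surgical pathology: there is no needle-guidance image.
- PSA response: location match is not applicable, so prompting on location cannot change the result.

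**How close the decision rule is**

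Inputs: assumed CLR 0.30, target lower bound 0.20, two-sided 95% normal approximation (protocol 10.1); success if the lower bound exceeds 0.2 for two of three readers (protocol 10.4.2.1).

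The plan's sample size reproduces: n = 1.96² × 0.30 × 0.70 / 0.10² = 80.67, rounded up to 81.

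Lower bound = x/81 − 1.96 × √[(x/81)(1 − x/81)/81]:

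- x = 23: 0.186, fails
- x = 24: 0.197, fails
- x = 25: 0.208, passes

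At the planned CLR of 30%, the expected count is 0.30 × 81 = 24.3. The exact binomial chance that one reader reaches 25 is 0.474. At a true CLR of 20% it is 0.014. A result at the planning value therefore falls close to the cutoff.

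**Illustration with assumed inputs only**

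Let s be the share of evaluable subjects verified by correlative imaging, and f the fraction of their false positives that become true positives because the image was seen. The documents give neither. With a true CLR of 20% in every tier, the apparent rate is p = 0.20 + 0.80 × s × f, and the chance of at least 25 of 81 for one reader is:

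| s | f = 0.05 | f = 0.10 | f = 0.20 |
|---|---|---|---|
| 0.3 | 0.027 | 0.049 | 0.129 |
| 0.6 | 0.049 | 0.129 | 0.443 |
| 0.9 | 0.082 | 0.265 | 0.783 |

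The range is wide, and the documents do not narrow it. If all three readers saw the same images, their errors would tend to go the same way, so the two-of-three rule would give less protection than it does with independent errors.

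**The case against.** The strongest reply is that protocol 6.4 lists what the core lab's readers receive between them, and the SAP then divides the work. The SAP itself uses the term central readers loosely: 5.1.1 speaks of central Truth Panel readers, and 8.4 has central readers judging follow-up assessments. Protocol 8.3 says the core lab evaluates images as applicable, and the only anatomic aid it names for the PET read is the scan's own CT. Both documents leave the detail of reading to the Charter. The SAP, under which the CLR is computed, already specifies the sound arrangement.

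Much of this stands. A reader might infer that the two documents cannot be reconciled. The pooled-group reading is possible, so that goes too far, but the protocol does not state that reading and nothing in 6.4, 8.2 or 8.3 keeps one group from the other's images. A reader might also infer that the primary endpoint is biased, or that all three readers lean in the favourable direction. The documents do not support either: no read is shown to have been done unmasked, the PSA tier has no location match, and masked pathology makes the biopsy direction uncertain.

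**Conclusion.** The discrepancy is real and bears on the independence of the primary endpoint. It holds as a conditional risk: if the core lab worked to the protocol wording, PyL readers could know the correlative result or the needle position when recording lesion locations. If it worked to SAP 4 and 5.1, the exposure does not arise. The Charter, which would settle this, was not available.

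The size cannot be derived from the documents. The step from 23 to 25 true positives out of 81 might be taken as an estimate of bias. It only shows how near the cutoff lies for one reader, and two extra matches from any source would do the same. The table of assumed shares likewise shows sensitivity, not an expected effect. The correction is worth making because the outcome may turn on a few matches and the change is one of wording.

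**What to change.** - Amend protocol 6.4, 8.2 and 8.3 to name the three PyL readers and the Truth Panel as separate groups.
- State that the PyL readers see only the PyL PET/CT with its own CT.
- Send biopsy-guidance and follow-up conventional images only to the Truth Panel or to other central reviewers distinct from the PyL readers. This includes the evaluability checks made during the trial.
- In SAP 5.1.1, correct the opening sentence that has the three PyL readers evaluating scans against the truth standard. In SAP 8.4, say which group judges follow-up assessments unevaluable.
- Confirm that the Imaging Review Charter says the same and that any reads already done complied.

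The cost is wording and a compliance check. The SAP already assumes two reader groups, and the sample size does not change. If completed PyL reads turn out to have been made with access to the other images, the cost is greater, because those reads would not meet the SAP's blinding.
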